7. MEASUREMENT OF EFFECT

7.1. Definitions

Tumor response and/or disease progression will be assessed by either physical exam measurements or CT scan (or other appropriate imaging modalities such as MRI consistent with the modality used prior to treatment) utilizing RECIST v1.1 criteria. Changes in only the largest diameter (unidimensional measurement) of the tumor lesions and in only the short axis of lymph node lesions are used in the RECIST v1.1 criteria. Assessments will be performed within 28 days of initiating study treatment, every 12 weeks thereafter.

7.1.1. Response Evaluable

A patient who initiates therapy per protocol, and is taken off study for disease progression or clinical progression, including death related to the underlying solid tumor malignancy (as determined by the treating oncologist) **will be** considered evaluable for response assessment. However, patients who have initiated therapy and who withdraw from the study for any reason other than clinical or radiographic progression, or death believed unrelated to their underlying solid tumor malignancy **will not be** considered evaluable for response. Reasons for patients who have initiated therapy, but are no longer evaluable for response could include (but are not limited to):

- The patient cannot tolerate therapy despite dose modifications, and there is no evidence of clinical/radiographic disease progression at the time of stopping therapy.
- An unexpected and/or unrelated medical illness, such as a stroke or myocardial infarction that is considered unrelated to the underlying solid tumor malignancy
- An unexpected trauma or death that is considered unrelated to the underlying solid tumor malignancy

7.1.2. Disease Parameters

7.1.2.1. Measurable Disease

The presence of at least one measurable lesion. Measurable lesions are defined as those that can be accurately measured in at least one dimension (longest diameter to be recorded) as:

- By chest x-ray: ≥ 20 mm;
- By CT scan or MRI: ≥ 10 mm

All tumor measurements must be recorded in millimeters (or decimal fractions of centimeters). Previously irradiated lesions are non-measurable except in cases of documented progression of the lesion since the completion of radiation therapy. Previously irradiated brain lesions will not be eligible to be target lesions.

Malignant Lymph Nodes: To be considered pathologically enlarged and measurable, a lymph node must be ≥ 15 mm in the short axis when assessed by CT scan (CT scan slice thickness recommended to be no greater than 5 mm) or MRI. At baseline and in follow-up, only the short axis will be measured and followed.

Bone lesions: Lytic bone lesions or mixed lytic-blastic lesions with identifiable associated soft tissue components that are 10 mm or larger in size and can be evaluated via cross-sectional imaging such as CT or MRI are considered measurable lesions per RECIST v1.1.

7.1.2.2. Non-measurable disease

All other lesions (or sites of disease), including small lesions (longest diameter <10 mm or pathological lymph nodes with ≥ 10 to <15 mm short axis), are considered non-measurable disease. Bone lesions, without associated soft tissue components, blastic bone lesions, leptomeningeal disease, ascites, pleural/pericardial effusions, lymphangitis cutis/pulmonitis, inflammatory breast disease, and abdominal masses (not followed by CT or MRI), are considered as non-measurable.

Note: Cystic lesions that meet the criteria for radiographically defined simple cysts should not be considered as malignant lesions (neither measurable nor non-measurable) since they are, by definition, simple cysts.

'Cystic lesions' thought to represent cystic metastases can be considered as measurable lesions, if they meet the definition of measurability described above. However, if non-cystic lesions are present in the same patient, these are preferred for selection as target lesions.

All measurements should be taken and recorded in metric notation, using a ruler or calipers. All baseline evaluations should be performed as closely as possible to the beginning of treatment and never more than 4 weeks before the beginning of the treatment. The same method of assessment and the same technique should be used to characterize each identified and reported lesion at baseline and during follow-up. Clinical lesions will only be considered measurable when they are superficial (e.g., skin nodules and palpable lymph nodes). For the case of skin lesions, documentation by color photography including a ruler to estimate the size of the lesion is required.

7.2. Methods of Measurement

CT and MRI are the best currently available and reproducible methods to measure target lesions selected for response assessment. Conventional CT and MRI should be performed with cuts of 10 mm or less in slice thickness contiguously. Spiral CT should be performed using a 5 mm contiguous reconstruction algorithm. This applies to tumors of the chest, abdomen and pelvis. For accurate objective response evaluation, ultrasound should not be used to measure tumor lesions. However, ultrasound is a possible alternative to clinical measurements of superficial palpable lymph nodes, subcutaneous lesions and thyroid nodules. Ultrasound might also be useful to confirm the complete disappearance of superficial lesions usually assessed by clinical examination. The same method of assessment and the same technique should be used to characterize each identified and reported lesion at baseline and during follow-up. Imaging-based evaluation is preferred to evaluation by clinical examination when both methods have been used to assess the antitumor effect of a treatment.

7.2.1. Baseline Documentation of "Target" and "Non-Target" Lesions

7.2.1.1. Target Lesions

All measurable lesions up to a maximum of 2 lesions per organ and 5 lesions in total, representative of all involved organs, should be identified as target lesions and recorded and measured at baseline. Target lesions should be selected on the basis of their size (lesions with the longest diameter) and their suitability for accurate repeated measurements (either by imaging techniques or clinically). It may be the case that, on occasion, the largest lesion does not lend itself to reproducible measurement in which circumstance the next largest lesion which can be measured reproducibly should be selected. A sum of the longest diameter (LD) for all target lesions will be calculated and reported as the baseline sum LD. The baseline sum LD will be used as reference by which to characterize the objective tumor response.

- Previously irradiated brain lesions will not be eligible to be selected as target lesions.
- If a patient has measurable disease outside of the brain, the lesion(s) outside of the brain will be selected as the target lesion(s).

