3.2. Inclusion Criteria

Patients must meet all the following inclusion criteria to be eligible for enrollment in the study:

1. Histologically or cytologically proven diagnosis of breast cancer with evidence of metastatic or locally advanced disease, not amenable to resection or radiation therapy with curative intent.
2. Documentation of ER-positive and/or PR-positive tumor ($\geq 1\%$ positive stained cells) based on most recent tumor biopsy (discuss with the Principle Investigator if results in different biopsies are discordant in terms of hormone receptor positivity) utilizing an assay consistent with local standards.
3. Documented HER2-negative tumor based on local testing on most recent tumor biopsy: HER2-negative tumor is determined as immunohistochemistry score 0/1+ or negative by in situ hybridization (FISH/CISH/SISH) defined by current ASCO/CAP (American Society of Clinical Oncology/College of American Pathologists) guidelines. Patients with equivocal HER2 in situ hybridization results according to current ASCO/CAP guidelines are eligible, as long as they have not received and are not scheduled to receive anti-HER2 treatment.
4. Must have progressed on (or been intolerant of) at least 2 lines of endocrine therapy in either the adjuvant or metastatic setting and progressed on (or been intolerant of) a CDK4/6 inhibitor.
5. Must have received no more than 4 lines of systemic therapy (for example, including but not limited to endocrine therapy, targeted therapy, biologic therapy, chemotherapy, or experimental therapy) for the treatment of breast cancer in the metastatic setting.
6. Premenopausal or postmenopausal female or male patients 18 years of age or older.
7. Measurable disease as defined by RECIST v1.1 criteria (tumor $\geq 1\text{ cm}$ in longest diameter on axial image on computed tomography (CT) or magnetic resonance imaging (MRI) or tumor $\geq 10\text{ mm}$ by caliper measurement on clinical exam and/or lymph node(s) $\geq 1.5\text{ cm}$ in short axis on CT or MRI) at baseline. Lytic bone lesions or mixed lytic-blastic lesions with an associated soft tissue component $\geq 10\text{mm}$ noted on CT or MRI are also included as per RECIST 1.1 criteria. Index lesions must not have undergone prior radiation therapy.

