7.4. RECIST v1.1 Response Criteria

7.4.1. Evaluation of Tumor Response-Measurable Disease

7.4.1.1. Complete Response (CR)

The disappearance of all known target lesions, determined by two observations not less than 4 weeks apart. There can be no appearance of new lesions.

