7.4.1.2. Partial Response (PR)

A 30% or more decrease in the sum of the LD of target lesions that have been measured to determine the effect of therapy by two observations not less than 4 weeks apart. There can be no appearance of new lesions.

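### Target lymph nodes are to be measured by short axis only, but the response sum and the PR, PD and SD rules use longest diameter for all target lesions, with no exception for nodes

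*Combined protocol and SAP*

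**What the plan says.** Two sets of statements in Section 7 deal with how a node is measured.

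- **Short axis.** Section 7.1 says: "Changes in only the largest diameter (unidimensional measurement) of the tumor lesions and in only the short axis of lymph node lesions are used". Section 7.1.2.1 says of malignant nodes: "At baseline and in follow-up, only the short axis will be measured and followed". To be measurable, "a lymph node must be ≥ 15 mm in the short axis"; Section 3.2 item 7 uses the same size for entry.
- **Longest diameter (LD).** Section 7.2.1.1 takes all measurable lesions as targets, up to two per organ and five in total, without excepting nodes. It continues: "A sum of the longest diameter (LD) for all target lesions will be calculated and reported as the baseline sum LD". That sum is the reference for response. PR in Section 7.4.1.2 is "A 30% or more decrease in the sum of the LD of target lesions". Sections 7.4.1.3 (PD, a rise of at least 20%) and 7.4.1.4 (SD) use the same sum.

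For CR, Section 7.4.1.1 requires: "The disappearance of all known target lesions, determined by two observations not less than 4 weeks apart". It gives no size limit for nodes. Section 7.1.2.2 lists pathological nodes of 10 to under 15 mm short axis as non-measurable disease.

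Sections 7.3 and 8.4.1 name RECIST v1.1 as the basis for response.

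**The concern.** A patient can enter with a node as the only measurable lesion, and that node is then the only target. For such a patient the plan asks for a sum of a dimension that it elsewhere says is not measured. A reader, or a case report form built from Sections 7.2.1.1 and 7.4, could reasonably record LD; one built from Sections 7.1 and 7.1.2.1 would record short axis.

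The sum decides PR, and so the primary endpoint. It also decides PD, and so feeds PFS, duration of response and the 24-week clinical benefit rate. Response is judged by the investigator (Section 7.3) and progression by the local site (Section 8.4.2.2). Five sites are listed, and the documents describe no central reading that would impose one convention.

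**Working it through.** **1. The decision rule that the classification feeds.** Inputs from Section 8.3: null ORR 0.095, alternative 0.20, stop at 2 or fewer of 30, reject the null at 8 or more of 50.

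P(reject | p) = sum over x = 3 to 30 of P(Bin(30, p) = x) × P(Bin(20, p) ≥ 8 − x).

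At p = 0.095 this is 0.0955 (stated limit 0.1); at p = 0.20 it is 0.8022 (stated power 0.8). The plan's figures reproduce and are not in dispute. Both sit close to their limits.

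**2. Can the two measurement rules disagree?** Change = (follow-up sum − baseline sum) / baseline sum. PR is −30% or lower; PD is +20% or higher. The documents contain no patient measurements, so every diameter below is assumed. Baseline is taken as the smallest earlier sum, and the confirming observation for PR is taken to agree.

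| Assumed lesions (mm) | Short axis for nodes | LD for all lesions |
|---|---|---|
| A. Liver 20 to 16; node short axis 16 to 8, LD 24 to 18 | 36 to 24: −33.3%, PR | 44 to 34: −22.7%, SD |
| B. Node only; short axis 18 to 12, LD 28 to 22 | −33.3%, PR | −21.4%, SD |
| C. Node only; short axis 18 to 14, LD 30 to 20 | −22.2%, SD | −33.3%, PR |
| D. Visceral 20 to 14; node short axis 16 to 13, LD 30 to 20 | 36 to 27: −25.0%, SD | 50 to 34: −32.0%, PR |
| E. Visceral 20 to 23; node short axis 15 to 20, LD 25 to 27 | 35 to 43: +22.9%, PD | 45 to 50: +11.1%, SD |

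A and B lose a response under LD, C and D gain one, and E moves the date of progression. In a node-only patient the two rules give the same percentage only if both axes change in the same proportion.

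**3. What a net shift in observed ORR would do.** The size of any shift is unknown. Putting assumed shifts into the formula in step 1:

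- Null case, 9.5% observed as 11.5%: false-positive rate 0.207; as 13.5%: 0.354.
- Alternative case, 20% observed as 18%: power 0.691; as 16%: 0.551.

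These show how sensitive the design is. They do not estimate this fault's effect.

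**4. The CR wording.** A target node starts at 15 mm or more in short axis. A fall to below 10 mm is a decrease of more than (15 − 10)/15 = 33.3%. If every nodal target falls below 10 mm and all other targets vanish, the short-axis sum has fallen by more than 33.3%, which already meets the size threshold for PR. With the sum on short axis, the CR wording therefore moves such a patient between CR and PR and leaves ORR (CR + PR) unchanged.

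**The case against.** The strongest reply is that the plan, read as a whole, has one answer. Section 7.1 describes what the governing criteria use for nodes: "in only the short axis of lymph node lesions are used in the RECIST v1.1 criteria". Sections 7.3 and 8.4.1 make those criteria govern response. Section 7.1.2.1 gives longest diameter as the general rule and then a specific rule for nodes, so LD in Sections 7.2.1.1 and 7.4 may be a general term with the nodal exception already made. The version history records that version 1.5 revised the measurement definitions towards RECIST 1.1, so LD may simply be left over. A site using LD for a node would have to record a dimension that Section 7.1.2.1 excludes.

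Most of this stands as evidence of intent: short axis is the likely meaning. It does not repair the definitions that are actually applied. Those say LD for all target lesions, and neither Section 7.3 nor Section 8.4.1 says which internal rule forms the sum.

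Three stronger readings should be resisted.

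- A reader might infer that sites will classify the same scans differently. The documents show only that they could.
- A reader might infer that ORR is biased in a known direction. Examples A to D go both ways, and no share of patients with nodal targets is given. That one patient can decide 2 v 3 of 30 or 7 v 8 of 50 is true of any doubt about classification.
- A reader might infer that the CR wording helps cause the PR/SD disagreement or lowers ORR. Step 4 shows that it does neither.

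**Conclusion.** The inconsistency is in the current text and bears on the primary endpoint. Sections 7.1 and 7.1.2.1 cannot be applied together with Sections 7.2.1.1 and 7.4.1.2 to 7.4.1.4 to a nodal target. If LD is used, a patient can change between PR and SD in either direction, or between SD and PD. The possibility is established by arithmetic on assumed diameters. Its frequency, and so its effect on ORR, is unquantified. It should be corrected as more than a clerical slip, although the likely intent is clear.

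The secondary point is narrower. As written, a patient whose nodal target shrinks below 10 mm but stays visible cannot be a CR. A reader might take 10 mm to be a CR limit already set in Section 7.1.2.2. That section only classifies nodes as non-measurable disease; it states no response limit, so the figure is an inference from it. The effect is confined to the CR/PR split. No decision rule uses CR alone, and the clinical benefit rate pools CR, PR and SD.

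**What to change.** - In Sections 7.2.1.1 and 7.4.1.2 to 7.4.1.4, replace the LD sum with a sum of diameters: longest diameter for non-nodal lesions, short axis for nodal lesions.
- Align the tumour-measurement case report form, so that each target is flagged nodal or non-nodal and the matching dimension is recorded.
- For any patient with a nodal target measured by LD, recalculate the baseline and follow-up sums from the stored scans.
- In Section 7.4.1.1, state the short-axis limit at which a nodal target counts as resolved for CR, and reconcile it with Section 7.1.2.2. Below 10 mm would be consistent with that section, but it has to be written as a response rule.

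The cost is a wording amendment, a form change and re-measurement for whichever patients are affected, a number the documents do not give. It adds no patients, visits or scans, and the design in Section 8.3 is unchanged.

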7.2.1.2. Non-Target Lesions

All other lesions (or sites of disease) including any measurable lesions over and above the 5 target lesions should be identified as non-target lesions and should also be recorded at baseline. Measurements of these lesions are not required, but the presence or absence of each should be noted throughout follow-up.

7.3. Assessment of Response by RECIST v1.1

RECIST v1.1 will be used by the Investigator as the primary measure for assessment of tumor response, date of disease progression, and as a basis for all protocol guidelines related to disease status.

7.4. RECIST v1.1 Response Criteria

7.4.1. Evaluation of Tumor Response-Measurable Disease

7.4.1.1. Complete Response (CR)

The disappearance of all known target lesions, determined by two observations not less than 4 weeks apart. There can be no appearance of new lesions.

7.4.1.2. Partial Response (PR)

A 30% or more decrease in the sum of the LD of target lesions that have been measured to determine the effect of therapy by two observations not less than 4 weeks apart. There can be no appearance of new lesions.

7.4.1.3. Progressive Disease (PD)

At least a 20% increase in the sum of the LD of target lesions, taking as reference the smallest sum LD recorded since the treatment started, or the appearance of one or more new lesions, and/or an unequivocal progression of non-target lesions.

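### Target-lesion progression is a 20% rise over the smallest sum with no absolute minimum, so in patients with small reference sums reading error can be recorded as progression

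*Combined protocol and SAP*

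**What the plan says.** **Progression.** Section 7.4.1.3 sets the target-lesion criterion as "At least a 20% increase in the sum of the LD of target lesions, taking as reference the smallest sum LD" since treatment began. New lesions and unequivocal non-target progression are separate routes. No minimum in millimetres appears there or elsewhere, and progression needs no second reading. CR and PR (7.4.1.1, 7.4.1.2) need two observations at least 4 weeks apart.

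**Lesion size and number.** Section 7.1.2.1 asks for "The presence of at least one measurable lesion", with the threshold "By CT scan or MRI: ≥ 10 mm"; Section 3.2 item 7 agrees. A baseline sum of 10 mm is therefore admissible. Section 7.2.1.1 takes as targets "All measurable lesions up to a maximum of 2 lesions per organ and 5 lesions in total".

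**Slice thickness.** Section 7.2: "Conventional CT and MRI should be performed with cuts of 10 mm or less in slice thickness contiguously", but "Spiral CT should be performed using a 5 mm contiguous reconstruction algorithm". Section 7.1.2.1, for lymph nodes only: "CT scan slice thickness recommended to be no greater than 5 mm".

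**Link to the standard.** Section 7.3: "RECIST v1.1 will be used by the Investigator as the primary measure for assessment of tumor response, date of disease progression". Sections 4.3.9, 7.6 and 8.4.2.2 also name RECIST v1.1, for continuing treatment, for defining progression and for PFS. Nothing says whether the rule written in 7.4.1.3 or the cited standard prevails if they differ.

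**The concern.** A purely relative rule over a running minimum asks for a very small change when the sum is small. The minimum also drifts down with chance low readings, so the next ordinary reading can look like growth.

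A patient can even be called progressed while still below baseline. A lesion that falls from 10 to 7 mm meets the PR threshold, and 8.4 mm at the next scan is then progression, although it is 16% smaller than at baseline. With whole-millimetre readings 9 mm is needed (2/7 = 29%; 8 mm is only 1/7 = 14%), which is still below baseline. If this happens before the second observation, the PR is never confirmed.

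The documented consequences are these:

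- Progression on the local reading is a PFS event (8.4.2.2).
- Progression before the CBR time point lowers CBR (8.4.2.3).
- Best response is recorded only until progression (7.5), so a later response does not count. Section 1.5 reports that most objective responses in the first-in-human study came after 3 months.
- Radiographic progression is also tied to withdrawal from treatment (4.3.9, 4.3.12).

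**Working it through.** **1. The plan's own design figure.** Section 8.3: stop with 2 or fewer responses in 30, reject the null with 8 or more in 50. With b the binomial probability,

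P(reject | p) = Σ (k = 3 to 30) b(k; 30, p) × P(Bin(20, p) ≥ 8 − k).

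At p = 0.095 this is 0.0955, and at p = 0.20 it is 0.802. The stated 0.1 and 0.8 reproduce, and nothing below changes them as computed.

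**2. Rise needed for progression** = 0.20 × reference sum.

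| Reference sum (mm) | 5 | 7 | 10 | 15 | 20 | 25 | 50 |
|---|---|---|---|---|---|---|---|
| Rise needed (mm) | 1.0 | 1.4 | 2.0 | 3.0 | 4.0 | 5.0 | 10.0 |

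A rise of 1–2 mm suffices only at sums of about 5–10 mm. A 5 mm floor binds only where 0.20 × sum < 5, that is, below 25 mm.

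**3. Hand check, one follow-up scan.** Take one lesion truly unchanged at 10 mm, with independent normal reading error of SD σ. Progression is called if X1 − 1.2·X0 ≥ 0. This difference has mean 10 − 12 = −2 and SD σ√(1 + 1.44) = 1.562σ. For σ = 0.5, 1.0 and 1.5 mm, the chance that a standard normal exceeds 2/(1.562σ) is about 0.5%, 10% and 20%.

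**4. Three restaging scans, by simulation.** The reference is the smallest reading so far. The baseline reading must be at least 10 mm, because otherwise the patient has no measurable disease. Reading SDs are assumptions; the documents give none.

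| Reading SD (mm) | 20% rule, unrounded | 20% rule, rounded to 1 mm | 20% and 5 mm, unrounded | 20% and 5 mm, rounded |
|---|---|---|---|---|
| 0.5 | 1.4% | 7% | 0% | 0% |
| 1.0 | 24% | 37% | 0.1% | 0.3% |
| 1.5 | 45% | 55% | 2.5% | 5% |

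Without the baseline condition, the 20% rule alone gives 2.7/37/61% unrounded and 13/49/67% rounded. Those figures are too high, because they count patients who would not be eligible.

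**5. Where the effect fades.** SD 1 mm per lesion, unrounded, three scans, no baseline condition:

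| Target lesions | No floor | 3 mm floor | 5 mm floor |
|---|---|---|---|
| one of 10 mm | 37% | 8% | 0.1% |
| one of 15 mm | 13% | 8% | 0.1% |
| two of 10 mm | 16% | 16% | 3% |
| one of 25 mm | 0.4% | 0.4% | 0.1% |
| five of 10 mm | 1.1% | 1.1% | 1.1% |

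The single 25 mm lesion still gains a little because a low reading takes the reference just under 25 mm.

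**The case against.** **The cited standard may already settle it.** Four sections name RECIST v1.1, and 7.4.1.3 sits under a RECIST v1.1 heading, so a site might apply the standard itself rather than the short text. This stands as a condition on the finding. It does not remove the need to act, because 7.4.1.3 is the definition that local readers will see and no order of precedence is given.

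**The worst case is not the typical case.** A reader might infer that a 1–2 mm difference ends follow-up for patients generally. It does so only at reference sums of about 10 mm or less. All measurable lesions up to five become targets, and 7.2.1.1 asks for lesions suited to repeated measurement. This stands.

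**Slice thickness.** A reader might set the 2 mm threshold against the permitted 10 mm cuts. Longest diameter is read on the axial image (3.2 item 7), so slice thickness is not in-plane precision. The 10 mm figure is for conventional CT and MRI, and spiral CT is set at 5 mm. Nor do the documents support a rule that a lesion must be twice the slice thickness. What remains is that 7.1.2.1 and 7.2 give different figures.

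**Consequences that go too far.** A reader might infer that false progression fixes best response as PD. Table 6 reserves that for patients with no earlier SD, PR or CR; after SD at the first scan, best response stays SD and simply cannot improve. A shortened duration of response is also only an inference, because 8.4.2.1 states no end event. The simulation covers unchanged disease, so it shows no quantified loss of responders and no error in the Simon design.

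**The 5 mm value is not from the documents.** That is true. It is offered as an example, and the 3 mm column above shows what a smaller floor would leave.

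**Conclusion.** The point holds for small reference sums. Followed as written, 7.4.1.3 lets ordinary reading error be recorded as progression when the reference sum is below 25 mm, and chiefly at about 10 mm or less. For one unchanged 10 mm lesion, the chance over three scans runs from about 1–7% to 45–55% as the assumed reading SD goes from 0.5 to 1.5 mm. With a 5 mm floor it runs from about 0% to 2.5–5%. PFS and CBR are affected directly. Best response can be affected because it stops at progression.

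The result rests on assumed reading SDs, independent normal errors, three scans and a single target lesion. The documents give no distribution of lesion sums, so the number of patients affected among the 50 cannot be stated. The effect is also conditional on the written rule governing over the cited standard. This is an endpoint definition worth correcting; it is not a defect in the sample size or decision rule.

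**What to change.** 1. In the endpoint definition in 7.4.1.3, require for target-lesion progression both the 20% rise and an absolute increase over the smallest sum, for example at least 5 mm. Leave the new-lesion and non-target routes unchanged.
2. State that this definition applies to PFS, CBR and best response.
3. Reconcile it with the RECIST v1.1 references in 4.3.9, 7.3, 7.6 and 8.4.2.2, and say which text prevails. The passages that tie continuing treatment to progression (4.3.9, 4.3.12) must be part of that reconciliation. How they are resolved is for the sponsor and investigators.
4. Reconcile the slice-thickness statements in 7.1.2.1 and 7.2.

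The cost is a few sentences in Section 7 and aligned cross-references. The downside is that target-lesion progression is declared slightly later in a few patients with very small sums. The sample size and decision rule stay as they are.
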